8.2 Handling of Potential Intercurrent Events

Potential intercurrent events considered in the Induction Study include 1) premature discontinuation of study drug and 2) use of UC-related rescue medications defined in Section 8.2.2. Intercurrent events will be handled using the following methods for the efficacy analysis:

8.2.1 Premature Discontinuation of Study Drug

If the subjects prematurely discontinued study drug but stayed in the study, data collected after premature discontinuation of study drug will be used, unless subjects received UC-related medications satisfying one or more of the following criteria,

- Usage of any biologics approved for UC (anti-TNF- α agents including infliximab, adalimumab, golimumab and biosimilars, vedolizumab and biosimilars, Ustekinumab and biosimilars)
- Usage of any JAK inhibitors approved for UC (including but not limited to tofacitinib)
- Usage of any total parenteral nutrition (TPN)
- Usage of any cytapheresis treatment
- Any Initiation or dose escalation of immunosuppressant compared to Week 0 of the Maintenance Study

- Any initiation or dose escalation of antibiotics compared to Week 0 of the Maintenance Study
- Any initiation or dose escalation of aminosalicylates compared to Week 0 of the Maintenance Study
- Any initiation or dose escalation of corticosteroids (Definitions in Section 8.2.2)
- Usage of investigational compounds

8.2.2 UC-Related Rescue Medications

The UC-related rescue medications intercurrent events during the study drug treatment period comprises of the following two intercurrent events,

1. UC-Related corticosteroids intercurrent events are defined as follows:
 - subjects not on UC-related corticosteroids (systemic or locally acting corticosteroids for UC) at Baseline who initiated UC-related corticosteroids during the Maintenance Study;
 - subjects on UC-related systemic corticosteroids at Baseline who had dosages increased to greater than the prednisone equivalent dose of corticosteroid at Baseline, or initiation of any rectal corticosteroids during the Maintenance Study regardless of rectal corticosteroid dose;
 - subjects on UC-related rectal corticosteroids at Baseline who have dosages increased to greater than the dose taken at Baseline, or initiation of any new type of rectal or any systemic corticosteroids during the Maintenance Study.
 - if a subject enters the Maintenance Study without corticosteroids, threshold dose of corticosteroids for censoring will be compared to the Baseline dose of the Induction Study. If subject enters the Maintenance Study with corticosteroids, threshold dose of corticosteroids for censoring will be compared to the dose at Baseline of the Induction Study or at baseline of the Maintenance Study, whichever of the two doses is higher.
2. UC-related non-corticosteroid rescue medications include systemic or rectal use of aminosalicylates, antibiotics and methotrexate. The intercurrent events are defined

as subjects who have initiation or dose escalation of any of these medications compared to Week 0.

The time point of the UC-related rescue medications intercurrent event is defined as the date when one of the intercurrent events above occurs for a subject. For categorical endpoints, subjects will be considered as "non-responder" at or after the occurrence of the UC-related rescue medication intercurrent event through the end of the Maintenance Study except for the As Observed (AO) analysis. For continuous endpoints, all measurements from the date of UC-related rescue medications intercurrent event through the end of the Maintenance Study will not be used in the analysis except for the As Observed (AO) analysis. Methods to handle visits after these intercurrent events are described in Section 8.3.2.

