5.2.3.3 Prohibited Therapy

The following are prohibited medications during the study:

Biologic Therapies

Subjects must have discontinued any biologic therapy prior to the first dose of study drug as specified in the washout procedures (Exclusion Criterion 14, Section 5.2.2). For all other biologic therapies the required washout period is at least five times the mean terminal elimination half-life of the medication prior to the first dose of study drug. No minimum washout prior to Baseline is required for a biologic therapy if an undetectable drug level measured by a commercially available assay is documented.

- All biologic therapy including but not limited to the following:
 - Etanercept;
 - Abatacept;
 - Anakinra;
 - Rituximab;
 - Natalizumab;
 - Tocilizumab;
 - Efalizumab;
 - Ustekinumab;
 - Belimumab;
 - Golimumab;
 - Vedolizumab;
 - Infliximab;
 - Adalimumab;
 - Certolizumab pegol
 - Secukinumab
- Other JAK inhibitors (e.g., tofacitinib [Xeljanz[®]], ruxolitinib [Jakafi[®]], baricitinib [Olumiant[®]], peficitinib, [Smyraf[®]], abrocitinib [PF-04965842], and filgotinib)

- **Vaccines**

If the subject and investigator choose to receive/administer live vaccines, these vaccinations must be completed (per local label) at least 30 days (8 weeks for subjects in Japan) before first dose of study drug (see Section 5.2.3 Prior and Concomitant Therapy). Live vaccinations are prohibited during study participation including at least 30 days (or longer if required locally) after the last dose of study drug.

- Examples of live vaccines include, but are not limited to, the following:
 - Monovalent live influenza A (H1N1) (intranasal);
 - Seasonal trivalent live influenza (intranasal);
 - Zostavax (herpes zoster, live attenuated);
 - Rotavirus;
 - Varicella (chicken pox);
 - Measles-mumps-rubella or measles-mumps-rubella-varicella;
 - Oral polio vaccine;
 - Smallpox;
 - Yellow fever;
 - Bacille Calmette-Guérin (BCG);
 - Typhoid (oral).

Administration of inactivated (non-live) vaccines is permitted prior to or during the study according to local practice guidelines. Examples of common vaccines that are inactivated, toxoid or biosynthetic include, but are not limited to, injectable influenza vaccine, pneumococcal, Shingrix (zoster vaccine, recombinant, adjuvanted) and pertussis (Tdap) vaccines.

Other Medications

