5.2.3.4 Rescue Therapy

At or after Week 4 in Substudy 3, subjects who demonstrate loss of response and require medical treatment but have not met the criteria to enter Study M14-533 Cohort 1, may

receive rescue therapy. Rescue therapy may be provided in the form of initiation or increased dosage, at the investigator's discretion, of allowed UC-related medications to treat new or worsening UC symptoms. The allowed UC-related medications are locally acting, oral, or intravenous corticosteroids, aminosalicylates, MTX or UC-related antibiotics.

Anti-diarrheals for control of diarrhea are not considered rescue treatment. Azathioprine (AZA), 6-mercaptopurine (6-MP), cyclosporine, tacrolimus, and thalidomide are prohibited medications during the study and cannot be used as rescue treatment.

Changes in UC-related concomitant medications should be documented in the appropriate eCRF. Rescue therapy should not be withheld even if subject does not meet the criteria for loss of response or before 4 weeks after entering Substudy 3 if in the opinion of the investigator, failure to prescribe them would compromise the subject's safety. Subjects may also be discontinued at any time based on the investigator's medical assessment.

For subjects receiving corticosteroids as a rescue treatment, the investigator is encouraged to initiate tapering based on the subject clinical response status.

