5.4 Removal of Subjects from Therapy or Assessment

5.4.1 Discontinuation of Individual Subjects

A subject may withdraw from the study at any time. The investigator may discontinue any subject's participation for any reason, including an adverse event, safety concerns or failure to comply with the protocol. Toxicity management criteria for events of serious infections, malignancy, cardiovascular events, gastrointestinal perforation, ECG abnormality, and select laboratory abnormalities are described in Section 6.1.7 Toxicity Management.

Subjects must have study drug discontinued immediately if any of the following occur:

- Clinically significant abnormal laboratory results or adverse events, which rule out continuation of the study medication, as determined by the investigator and the AbbVie TA MD.
- The investigator believes it is in the best interest of the subject.

- The subject requests withdrawal from study drug or the study.
- Inclusion and exclusion criteria violation was noted after the subject started study drug, when continuation of the study drug would place the subject at risk as determined by the AbbVie TA MD.
- Introduction of prohibited medications or dosages when continuation of the study drug would place the subject at risk as determined by the AbbVie TA MD.
- Subject is non-compliant with TB prophylaxis (if applicable) or develops active TB at any time during the study.
- The subject becomes pregnant while on study medication.
- Subject is significantly non-compliant with study procedures which would put the subject at risk for continued participation in the trial as determined by investigator or the AbbVie TA MD.
- Serious infections (e.g., sepsis) which cannot be adequately controlled by anti-infective treatment or would put the subject at risk for continuation of the study drug.
- Malignancy, except for localized NMSC or carcinoma in-situ of the cervix
- Subject develops a gastrointestinal perforation (other than appendicitis or mechanical injury)
- Confirmed diagnosis of deep vein thrombosis, pulmonary embolus or non-cardiac, non-neurologic arterial thrombosis

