8.3.1 Categorical Endpoints

For binary efficacy endpoints, missing data will be handled using the following approaches:

- The primary approach for handling missing data will be **Non-Responder Imputation** while incorporating Multiple Imputation (MI) to handle missing data due to **COVID-19** (NRI-C).
- The NRI-C will categorize any subject who does not have an evaluation during a pre-specified visit window (either due to missing assessment or due to early withdrawal from the study) as a non-responder for the visit. The only exception is that missing data due to COVID-19 infection or logistical restrictions related to the COVID-19 pandemic will be handled by Multiple Imputation (MI). At each visit, subjects will be characterized as responders or non-responders based on MI imputed values if missing due to COVID-19; otherwise, subjects will be considered as non-responders for missing due to other reasons in the NRI-C approach. In addition, at and after the UC-related rescue medications intercurrent event (see Section 8.2), subjects will be counted as non-responders.
- A sensitivity analysis will use **NRI** with **No** special data handling for missing due to **COVID-19** (NRI-NC).
- NRI-NC will be performed in the same way as NRI-C without the exception above. Missing due to COVID-19 infection or logistical restrictions will also be counted as non-responders. Subjects at or after the occurrence of the UC-related rescue medications intercurrent event will still be counted as non-responders. This is the same method as the "NRI" defined in the protocol.
- Hybrid Multiple Imputation Method (HMI): Sensitivity analysis will be performed using hybrid multiple imputation method for the primary endpoint.

Subjects who discontinue study drug prior to Week 52 due to lack of efficacy or AEs and have no available measurements will be considered as "non-responder" for clinical remission. Subjects who discontinue for other reasons and have no available measurements, or subjects who has missing Week 52 evaluations will be categorized according to the data from multiple imputations. In addition, at and after the UC-related rescue medications intercurrent event (see Section 8.2), subjects will be counted as non-responders.

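### The Substudy 3 SAP treats biologics, JAK inhibitors and other prohibited UC treatments as disqualifying only after study drug is stopped, and return-to-baseline imputation does not reach them

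*SAP*

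**What the plan says.** Substudy 3 SAP 8.2.1 covers subjects who stop study drug but are still being followed up: "data collected after premature discontinuation of study drug will be used, unless subjects received UC-related medications satisfying one or more of the following criteria". The list that follows names approved biologics and JAK inhibitors, parenteral nutrition, cytapheresis, investigational compounds, and starting or escalating immunosuppressants, antibiotics, aminosalicylates or corticosteroids.

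SAP 8.2.2 defines the rescue event more narrowly. It opens: "The UC-related rescue medications intercurrent events during the study drug treatment period comprises of the following two intercurrent events". The first component is corticosteroids. The second is: "UC-related non-corticosteroid rescue medications include systemic or rectal use of aminosalicylates, antibiotics and methotrexate".

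SAP 8.3.1 uses that event to force failure on binary endpoints: "at and after the UC-related rescue medications intercurrent event (see Section 8.2), subjects will be counted as non-responders". The introduction to 8.2 says that rescue medications are those defined in 8.2.2, so this cross-reference does not bring in the longer 8.2.1 list.

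For continuous endpoints, 8.3.2 first imputes every missing value under MAR. RTB Step 2 and the DBMI delta then act only on values missing because of rescue use. Appendix E attaches RTB to IE2 (rescue) and names no method for data dropped after IE1 (discontinuation).

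Protocol 5.2.3.3 introduces its list, which includes biologics and other JAK inhibitors, with "The following are prohibited medications during the study". Protocol 5.2.3.4 says of azathioprine, 6-MP, cyclosporine, tacrolimus and thalidomide that they "are prohibited medications during the study and cannot be used as rescue treatment". Under Protocol 5.4.1, however, the trigger for stopping study drug is conditional: "Introduction of prohibited medications or dosages when continuation of the study drug would place the subject at risk".

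**The concern.** The sponsor has already judged, in 8.2.1, that these treatments make later efficacy data unusable. That judgement applies only once study drug has stopped. On study drug, a subject who escalates an aminosalicylate is a failure. A subject who adds infliximab, with no 8.2.2 medication, keeps the observed Week 52 result.

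Prohibition does not close the gap, because 5.4.1 does not require study drug to stop in every case. Protocol 7.0 makes use of prohibited treatment a reportable deviation and SAP Appendix A tabulates it, so the plan expects that some may occur.

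For IBDQ and FACIT-F (ranked secondaries 8 and 12), starting a biologic off drug gets a MAR value, while starting an antibiotic on drug gets return-to-baseline. If the MAR mean change is an improvement, the more potent added treatment gets the more favourable assumption.

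These endpoints are under type I error control, so the handling should not depend on whether study drug was still being taken, or be settled after database lock.

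**Working it through.** **1. The plan's own figure.** Inputs (SAP 2.4): 150 per arm, remission 12% against 40%, two-sided Fisher's exact test at 0.025, stated power above 95%. Exact enumeration gives 99.97%, so the stated figure reproduces.

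**2. One treatment through the rules.** Take a subject who uses a biologic and no 8.2.2 medication.

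| | On study drug | Off study drug, still in study |
|---|---|---|
| Binary | No 8.2.2 event; the observed Week 52 value counts, so remission is possible under NRI-C, NRI-NC and HMI | Data dropped (8.2.1); non-responder under NRI-C unless missing due to COVID-19 |
| IBDQ, FACIT-F | Observed value used | Value dropped; MAR draw in Step 1; not replaced in Step 2; not shifted by DBMI |

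The same holds for JAK inhibitors, parenteral nutrition, cytapheresis, investigational compounds and non-methotrexate immunosuppressants. HMI has a related gap: an off-drug user who stopped for reasons other than lack of efficacy or an adverse event could be multiply imputed and counted as a remitter.

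**3. Period wording in 8.2.2.** The opening sentence limits the event to the period on study drug. The first corticosteroid bullet covers subjects "who initiated UC-related corticosteroids during the Maintenance Study", which is longer. Protocol 8.1.3 refers to rescue use in Substudy 3 as a whole. It is therefore unclear whether RTB reaches corticosteroids, aminosalicylates, antibiotics or methotrexate started off drug. Under NRI-C the binary result is non-response on either reading; only the continuous imputation could differ.

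**4. Size, binary endpoints.** One subject is 1/150 = 0.67 points; three are 3/150 = 2.0 points. Rescoring k active-arm remitters from the planned 60/150, with placebo at 12% (18/150):

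| k | Active arm | Difference (points) | Fisher power |
|---|---|---|---|
| 0 | 60/150 | 28.0 | 99.97% |
| 1 | 59/150 | 27.3 | 99.95% |
| 3 | 57/150 | 26.0 | 99.88% |
| 5 | 55/150 | 24.7 | 99.73% |

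If the rescored subjects were all on placebo, the difference would instead rise to 28.7, 30.0 and 31.3 points for k = 1, 3 and 5. With observed counts of 60/150 and 18/150, the Fisher p-value stays below 0.025 until k = 27.

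Ranked secondaries 2 and 3 are restricted to subjects who entered in remission. The documents do not give that share. Assuming 30% to 50% of an arm (45 to 75 subjects), one subject is 1/45 = 2.2 points to 1/75 = 1.3 points.

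**5. Size, IBDQ.** The shift in the treatment difference is m × k / 150, where m is the MAR mean change replaced by a return-to-baseline mean of 0 and k is the net imbalance between arms. Both are assumed.

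- m = 40, k = 1: 40/150 = 0.27 points.
- m = 60, k = 3: 180/150 = 1.2 points.
- Against the SAP's 16-point IBDQ response threshold (Section 3.3): 0.27/16 = 1.7%; 1.2/16 = 7.5%.

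A much wider assumption, 1% to 10% of one arm with m of 30 to 50, gives 0.01 × 30 = 0.3 to 0.10 × 50 = 5.0 points. FACIT-F was not quantified.

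**The case against.** The strongest reply is that the estimand is stated openly, cites 8.2.2, and is estimated as written, so this is only a preference for a wider rescue definition. The on-drug case is also narrow. The subject must take a prohibited treatment, stay on blinded drug, use no listed rescue and be in remission at Week 52. The protocol directs worsening subjects to permitted rescue or, after confirmed loss of response, to Study M14-533. SAP 8.4.4 adds an analysis that excludes important deviators, and As Observed uses the values collected. On the continuous side, off-drug biologic users are handled like other dropouts, who also get MAR draws.

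Much of this stands. Use is probably rare, the estimate does match the written estimand, and for the medication classes in 8.2.2 the binary score under NRI-C is the same on and off drug.

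Three parts do not answer the point. The 8.4.4 analysis is supplementary, covers only the primary endpoint, takes its criteria from a separate classification plan, and removes subjects instead of scoring them as failures. As Observed applies neither return-to-baseline nor a delta. The dropout comparison is weak, because these values are set aside on account of a disqualifying treatment, which is the reason the SAP gives 8.2.2 users return-to-baseline.

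**Conclusion.** The inconsistency is real and follows from the text. The same prohibited treatment is ignored on study drug and disqualifying off it, and the return-to-baseline rule misses the off-drug users. The period wording in 8.2.2 also needs reconciling.

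The consequence is one of endpoint meaning rather than of the trial's outcome. Binary differences move by 0.67 to 2.0 points for a net imbalance of 1 to 3 subjects. The IBDQ difference moves by 0.27 to 1.2 points on the assumed inputs, and by up to 5.0 on the widest range tried. The direction depends on which arm uses the treatments: on-drug use in an active arm inflates the difference, and on placebo it shrinks it. The documents give no user counts, no MAR mean change and no share entering in remission, so these sizes are illustrations. The change should be made because it is cheap and settles the rule before unblinding.

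**What to change.** - In SAP 8.2, define one list that applies on or off study drug: the 8.2.2 medications plus every item in 8.2.1. Score users as non-responders on binary endpoints from the date of use, under NRI-C, NRI-NC and HMI.
- In 8.3.2, apply RTB Step 2 and the DBMI delta to continuous values set to missing after any listed treatment.
- Align IE1 and IE2 in Appendix E, and the estimand text in 2.1, 8.4.1 and 8.6 that cites 8.2.2.
- Reconcile the two period statements in 8.2.2 with each other and with Protocol 8.1.3.

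The cost is SAP wording and flags derived from concomitant medications and treatments already recorded; no new data are needed. The rescue event in the estimand becomes slightly wider, and a few more subjects are classed as failures. These are analysis flags only and do not change patient management.

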8.3 Handling of Missing Data

Missing data could occur due to various reasons, including missing visits/assessments, early withdrawal from the Maintenance Study, or missing due to COVID-19 infection or logistical restrictions. Assessments on or after the date of UC-related rescue medication intercurrent event will be excluded from analyses, and methods to handle missing data will be applied for these visits.

The COVID-19 pandemic is interfering with the conduct of many ongoing trials, with potential impacts on treatment duration and the collection, analysis and the interpretation of clinical trial data. Some protocol-specified visits in the clinical trials may be impacted due to COVID-19 infection or logistical restrictions during the pandemic. For example, some scheduled visits may be missed due to self-quarantine or local government restrictions on travel; some visits may also be delayed or canceled due to healthcare resource constraints during the pandemic. Impacted visits due to COVID-19 will be recorded in the database. The probability of having missed visits and missing data due to COVID-19 infection or logistical restrictions related to the COVID-19 pandemic can be reasonably assumed to be unrelated to the unobserved values. Therefore, for the purpose of statistical analysis, it is reasonable to assume that these missing data are missing at

random (MAR) and the statistical models that require MAR assumption are appropriate. The intent is to provide reliable estimates of the treatment effects under the scenario without the impact of COVID-19 pandemic.

Handling of missing data for the efficacy analyses is described below.

8.3.1 Categorical Endpoints

For binary efficacy endpoints, missing data will be handled using the following approaches:

- The primary approach for handling missing data will be **Non-Responder Imputation** while incorporating Multiple Imputation (MI) to handle missing data due to **COVID-19** (NRI-C).
- The NRI-C will categorize any subject who does not have an evaluation during a pre-specified visit window (either due to missing assessment or due to early withdrawal from the study) as a non-responder for the visit. The only exception is that missing data due to COVID-19 infection or logistical restrictions related to the COVID-19 pandemic will be handled by Multiple Imputation (MI). At each visit, subjects will be characterized as responders or non-responders based on MI imputed values if missing due to COVID-19; otherwise, subjects will be considered as non-responders for missing due to other reasons in the NRI-C approach. In addition, at and after the UC-related rescue medications intercurrent event (see Section 8.2), subjects will be counted as non-responders.
- A sensitivity analysis will use **NRI** with **No** special data handling for missing due to **COVID-19** (NRI-NC).
- NRI-NC will be performed in the same way as NRI-C without the exception above. Missing due to COVID-19 infection or logistical restrictions will also be counted as non-responders. Subjects at or after the occurrence of the UC-related rescue medications intercurrent event will still be counted as non-responders. This is the same method as the "NRI" defined in the protocol.
- Hybrid Multiple Imputation Method (HMI): Sensitivity analysis will be performed using hybrid multiple imputation method for the primary endpoint.

Subjects who discontinue study drug prior to Week 52 due to lack of efficacy or AEs and have no available measurements will be considered as "non-responder" for clinical remission. Subjects who discontinue for other reasons and have no available measurements, or subjects who has missing Week 52 evaluations will be categorized according to the data from multiple imputations. In addition, at and after the UC-related rescue medications intercurrent event (see Section 8.2), subjects will be counted as non-responders.

- As Observed (AO): The AO analysis will not impute values for missing evaluations, and thus a subject who does not have an evaluation on a scheduled visit will be excluded from the AO analysis for that visit. AO will include all values collected in the study regardless the occurrence of UC-related rescue medication intercurrent event.

Details of Multiple Imputation (MI) for NRI-C and HMI: Markov Chain Monte Carlo (MCMC) will be first applied to augment data into monotonic missing pattern, where applicable, and PROC MI will be used to generate 30 datasets using the regression method. The variables to be included in the imputation model are: treatment group, stratification factors (Bio-IR status (Bio-IR or Non-Bio-IR) at the Baseline of the Induction Study, clinical remission status at Week 0 (yes or no), and corticosteroid use at Week 0 (yes or no)), Baseline measurement, and if applicable, post-baseline measurements at each visit up to the end of the analysis period. The random seed for MCMC and the random seed for PROC MI are specified in [Appendix D](#). The imputed post-baseline measurements will be rounded to the same precision as the observed data before the determination of responder status. Subjects will be characterized as responders or non-responders based on MI imputed datasets. Using the CMH model adjusted by stratification factors (Bio-IR status (Bio-IR or Non-Bio-IR) at the Baseline of the Induction Study, clinical remission status at Week 0 (yes or no), and corticosteroid use at Week 0 (yes or no)), the imputed endpoints will be analyzed using each of the 30 datasets. SAS PROC MIANALYZE will be used to generate the final treatment difference between each upadacitinib treatment group and placebo group and statistical inference of the risk difference, including hypothesis testing and 95% CI using Rubin's rule and T-distribution.³ [REDACTED]

